### Field Trial outcome variables

Sleep measurements including Total Sleep Time, Fragmentation Index, Wake After Sleep Onset, and Subjective Sleep Quality will be measured during the Baseline block and during the Intervention block. Sleep episodes in all participants will take place at home during off-shift times and will be recorded using wrist actigraphy and daily sleep e-diaries (which will be completed in the first hour after waking from the main sleep episode).

Subjective Alertness During both the Baseline and Intervention blocks, participants will complete an alertness task on the iPad three times per night shift: Once just before the night shift, once during their shift break, and once immediately following the night shift. The alertness assessment will consist of the Karolinska Sleepiness Scale (KSS) and a non-numeric bipolar (sleepy-alert) Visual Analog Scale (VAS).

Sustained Attention During both the Baseline and the Intervention Blocks, participants will complete a psychomotor vigilance task on the iPad three times per night shift: Once just before the night shift, once during their shift break, and once immediately following the night shift. The psychomotor vigilance task (PVT) is a 5-minute validated test of visual reaction time (RT) in which the participant is asked to maintain the fastest possible RTs to a simple visual stimulus.

Subjective Mood During both the Baseline and the Intervention Blocks, participants will complete a mood questionnaire on the Ipad three times per night shift: Once just before the night shift, once during their shift break, and once immediately following the night shift. Non-numeric bipolar (happy-sad) Visual Analogue Scales (VAS) will be used to assess subjective well-being and mood.

Fatigue, Inter-Shift Recovery, Subjective Stress and Quality of life will be assessed by questionnaire on the iPad immediately after the third night shift in the Baseline block and after the third night shift in the Intervention block (151, 152, 124).

Physiological Stress will be assessed by collecting a saliva sample immediately after the third night shift in the Baseline block and after the third night shift in the Intervention block to measure cortisol in subjects who live in the greater Boston area. Cortisol will be assayed in the Brigham Research Assay Core.

**General Methods for Shift Worker Survey.** To examine factors related to individual differences in the ability to adopt the sleep strategy, we will use a web-based survey consisting of ~70 questions developed and administered using REDCap. REDCap is a free, secure, web-based application for building and managing online surveys and databases. The complete questionnaire will take approximately 20-30 minutes to complete.

To understand the individual differences in sleep patterns adopted by shift workers, both in timing and in duration, and their ability to adjust sleep schedules, we will include demographic factors, circadian factors, questions of sleep in general and specific to night shifts, use of countermeasures, questions about non-work and work activities, and quality of life. We have selected factors which have been reported to be associated with inter-individual differences in adaptability to shift work and/or vulnerability to sleep loss, and therefore may contribute to the ability to adopt different sleep schedules in order to understand the barriers to achieving an 8-h sleep episode when working nights (72-76, 78, 117-119).

We will use questionnaires widely used in sleep research to assess morningness/circadian preference (120), flexibility of sleeping habits, vigor [i.e., the ability to overcome drowsiness (121, 122)], screening for shift work disorder (123), and qualty of life (124). We will also examine environmental factors (e.g. barriers/facilitators) that may be related to the feasibility of an individual being able to adopt an 8-h sleep episode, such as work hours, second jobs, work schedule (rotation and speed of rotation), type of occupation, commute time, and home sleep environment (noise, light).

For individuals who may not have access to a computer, we will provide a paper copy of the questionnaire to fill out and return.

**General Methods for Focus Groups.** The goal of the virtual focus groups is to gain information on the feasibility and acceptability of the fixed 8-h sleep schedule from the participants' perspective. We will seek to learn more information about the current sleep strategies they use on a regular basis, and both the facilitating and challenging aspects of the fixed-sleep countermeasure (e.g., individual, intrapersonal and organizational barriers to implementation of fixed 8-h sleep, recommended modifications to the fixed 8-h sleep schedule that would make it more user-friendly while maintaining scientific validity). Each of the virtual focus groups will consist of 4-6 individuals to stimulate thoughtful and dynamic discussion without leaving participants out. Separate focus groups for participants from the Field Trial and the Shift Worker Survey will be carried out to address the different issues of the two groups. Focus group scripts will be created and used to guide and moderate the discussions. Each focus group will last 60-90 minutes, and will be digitally-recorded and professionally transcribed. The 2018-P-002341 Detailed Protocol v5 2020\_09\_25

remote focus groups will be facilitated through secure videoconferencing (via HIPAA-compliant & MGB-approved Zoom) by [name] (Co-Investigator), who is a nursing professor with extensive experience in facilitating focus groups of nursing staff (83-85, 158).

## VI. BIOSTATISTICAL ANALYSIS

### VI. a) Data variables, b) Study endpoints, c) Statistical methods

**Analysis of objective sleep duration and quality, and subjective sleep quality in the Field Trial.** Sleep data will be calculated in all participants from both blocks (Baseline vs. Intervention) using actigraphy. Duration of sleep (total sleep time, TST), number of awakenings, fragmentation index (FI) during the major sleep episode and subjective sleep quality from the e-diaries may be used as outcome measures to address Aim 1. After descriptive analyses, we may use linear and generalized linear mixed models to analyze main and interaction effects for factors condition (randomization group: ad lib sleep, 8-h afternoon-evening sleep, or 8-h free sleep) and shift (Baseline: B-Night 2, B-Night 3; Intervention: I-Night 2, I-Night 3). To account for inter-individual differences, we may incorporate into our statistical model a random intercept statement allowing for means to vary between participants. We will compare within subjects (shift) and between groups (condition).

**Field Trial analysis of performance and subjective alertness (Aim 2).** Each of the tests will be administered using an iPad app. Initial processing of tests will be calculated automatically (e.g., exact time of administration, scoring of alertness scales; mean and median reaction time; number of lapses, shortest (fastest 10%) and longest (slowest 10%) reaction times on PVT]. Following the descriptive measures, analyses of RT and lapses and subjective alertness data may be performed using linear and generalized linear mixed models to analyze main and interaction effects for factors condition (randomization group, as above) and shift (as above) with participant as a random effect.

**Exploratory analysis of subjective stress and fatigue, recovery, mood, quality of life, and physiological stress in the Field Trial (Aim 2a).** Scores of acute subjective fatigue, inter-shift recovery, subjective stress, and quality of life will be calculated from the questionnaire administered at the end of Baseline and the end of Intervention. Mood will be assessed from visual analog scales administered three times per shift on nights 2 and 3 in the Baseline and Intervention blocks. Physiological stress will be assessed by analyzing cortisol levels in the optional saliva samples collected immediately after the third night shift in the Baseline and Intervention blocks. We will compare data from the Baseline to data from the Intervention for the three groups using linear and generalized linear mixed model analysis with factors condition (randomization group) and block (Baseline or Intervention) and incorporating a random intercept statement allowing for means to vary between participants.

**Field Trial exploratory analysis of scheduled 8-h afternoon-evening sleep vs. 8-h free sleep (Aim 2b).** We may compare results described above (sleep, performance and alertness, subjective stress, fatigue, recovery, mood, quality of life, and physiological stress) between the two scheduled sleep groups to determine whether the timing of an 8-h sleep episode has a significant impact on any of the outcomes. For this analysis, data from the 8-h free sleep group will first be examined for the time of day at which it occurred. Those participants who self-selected an afternoon-evening sleep episode will be classified with the 8-h afternoon-evening sleep group. We will carry out the analyses described above using linear mixed model analysis with factors condition (randomization group) and block (Baseline or Intervention) or night, incorporating a random intercept statement allowing for means to vary between participants.

**Analysis of the Shift Worker Survey.** (Specific Aim 3). The initial scoring of standard questionnaires and processing of data will be calculated automatically in REDCap. Descriptive analyses for all factors of interest will be calculated, as well as the reported ability to adhere to an 8-h free sleep/ 8-h afternoon-evening sleep schedule. To understand what individual differences contribute to shift workers' sleep patterns and ability to comply with an 8-h sleep schedule, we may conduct inferential statistics including bivariate and multivariate analyses on factors related to their ability to adopt the 8-h free sleep/8-h afternoon-evening sleep. Bivariate analyses (ANOVA and cross-tabulation) will be used to interpret the correlation between each factor and the outcome (ability to adhere to 8-h afternoon-evening sleep; ability to adhere to 8-h free sleep; inability to adhere to 8-h sleep).

Multivariable analysis (logistic regression analysis) and multivariate analysis (for example, structure equation modeling) may be used to test potential predictors of the outcome.

**Focus Group analysis** (Specific Aim 3). Data from this aim will be qualitative in nature. Focus group transcripts will be imported into NVivo11 or similar software for analysis. We will reorganize, reduce, and categorize the qualitative data based on common themes, and use content analysis to identify recurrent themes (157, 159). The code and quotes will be discussed by the research team to resolve discrepancies through interpretive discussions, consensus building, and refinement of code definitions as needed. The data will be independently coded by the investigators and compared to achieve consistency and conformability. The research team may send the focus group analysis results to participants to verify the codes and confirm the interpretive validity (159).

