The Intervention Block is similar to the Baseline Block, consisting of at least three consecutive 8-h night shifts, with the participants wearing an activity monitor, maintaining a daily sleep e-diary, and rating alertness, mood and attention three times per night shift using a mini iPad provided by the investigators. At the end of the first night shift, the participant will be told about their randomization group. In the control group (Group A), participants will not be given any instructions about the timing or duration of their sleep, but will be instructed to follow their usual night shift sleep routine. In the 8-h afternoon-evening sleep intervention group (Group B), participants will be instructed to go to bed between 13:00 and 14:00 (depending on their individual commute time) and to remain in bed attempting to sleep for 8 hours (until 21:00-22:00) before the next two night shifts. In the 8-h free sleep group (Group C), participants will be instructed to remain in bed for 8 continuous hours before the next two night shifts, but will not be given any instruction regarding which 8 hours they should sleep. Immediately following the last night shift, the participant will have the option to take a saliva sample to measure their stress level (cortisol), and they will complete a follow-up questionnaire where their fatigue, recovery, stress, and quality of life will be reassessed to investigate any exploratory short-term changes resulting from the intervention schedule. After completion of the two blocks, the participant will send back the activity monitor and iPad in a prepaid secured return package by mail or an investigator will arrange to meet with the participant to retrieve the activity monitor, iPad, and cortisol sample. Within 3 months after completion of the study blocks the participant will be invited to take part in a virtual Focus Group by secure videoconferencing (via HIPAA-compliant & MGB-approved Zoom).

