#### **COMMON**

**VII. d. Psychosocial (non-medical) risks.** Participants randomized into the 8-h scheduled sleep groups will be required to remain in bed attempting to sleep for 8 h following two successive night shifts. While they may feel frustrated with this if they cannot sleep, there is no long-term risk associated with this, and we anticipate that most participants will actually receive more sleep than they would typically get with ad lib sleep.

-It is possible that the participants randomized to the 8-h afternoon-evening sleep group will feel sleepy from the time they get off the night shift until the early afternoon scheduled bed time, which they may find frustrating. Due to the likelihood that participants randomized to the 8-h afternoon-evening sleep group will be awake for 24 or more hours after the first night shift in the Intervention week, they will be advised to use extra caution if they take part in any safety-sensitive activities that would put them at risk for an accident. All participants will be informed that they should use whatever countermeasures they routinely use to keep them safe (e.g., caffeine) and that they may withdraw from the study at any point that they feel the study conditions are too difficult

-There are minimal risks to participating in the Shift Worker Survey. Participants may experience some psychological discomfort responding to personal questions such as those about stress. Participants may choose not to answer any questions that they are not comfortable with. REDCap allows us to segregate identifiable information from the survey responses, and only the PI and one other study team member will have access to the identifiable information. There will be a code to link between the identifiable information and the survey data.

-There are minimal risks to participating in the virtual Focus Groups by secure videoconference. There is a small risk of feeling loss of confidentiality during focus group discussions. Participants will be asked to use an “alias” instead of their real name during focus group discussions. Audio recordings of focus group discussions will be destroyed upon completion of the study. No identifying information will be on the focus group transcript.

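### Total sleep time is calculated from actigraphy while assignment sets time in bed, so wake scored as sleep can inflate the B–A difference, and no planned analysis would show by how much

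*Combined protocol and SAP*

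**What the plan says.** The analysis section (VI.a–c) takes the objective Aim 1 outcomes (TST, number of awakenings, fragmentation index) from one instrument: "Sleep data will be calculated in all participants from both blocks (Baseline vs. Intervention) using actigraphy". Its only analytic use of the diary is that "subjective sleep quality from the e-diaries may be used as outcome measures to address Aim 1". The list under Field Trial outcome variables is wider. It says that sleep episodes "will be recorded using wrist actigraphy and daily sleep e-diaries", and it names wake after sleep onset (WASO), which the Aim 1 analysis text does not take up. Time in bed and sleep efficiency are outcomes in neither place. No scoring rule, rest-interval rule or sensitivity analysis for actigraphy is given.

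The arms differ by design in time in bed (Section V, Intervention Block). Group B is told "to remain in bed attempting to sleep for 8 hours". In Group C, "participants will be instructed to remain in bed for 8 continuous hours before the next two night shifts". In Group A, "participants will not be given any instructions about the timing or duration of their sleep", and they "will be instructed to follow their usual night shift sleep routine". Section VII.d foresees wakefulness in bed in the 8-hour groups: "While they may feel frustrated with this if they cannot sleep".

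**The concern.** Actigraphy infers sleep from lack of movement, so a person lying still but awake can be scored as asleep. An instruction to stay in bed for 8 hours whether or not sleep comes creates more opportunity for that error in B and C than in A, where a participant who wakes is free to get up. The error would push TST in the direction that Aim 1 predicts.

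Randomisation gives no protection, because the difference arises after assignment and through it. The baseline block does not help either. All arms follow their habitual schedule there, so the added time in bed occurs only in the Intervention block of B and C and falls in the condition-by-shift interaction that the mixed model examines. A larger sample would only estimate the biased difference more precisely.

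At stake is how far a positive B–A difference in TST supports the conclusion that Group B slept longer rather than lay still longer.

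**Working it through.** **Inputs from the documents.** SD of TST 84.4 min, 25 per group, α = 0.05, power 0.90 (printed as β = 0.9), detectable difference 78 min (all Section VI.d). Time in bed in B and C is 8 h = 480 min (Section V).

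**Inputs not in the documents, so assumed.** Group A time in bed of 420 or 360 min; share of the extra in-bed wake scored as sleep (1 − specificity) of 20% to 60%; equal true sleep in A and B, so that every extra minute in bed is wake.

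**Step 1: the plan's own figures.**
- n = 2(1.960 + 1.282)² × SD²/difference².
- TST: 2 × 10.507 × 84.4²/78² = 24.6, so 25 per group.
- Fragmentation index: 2 × 10.507 × 39.9²/37² = 24.4, so 25 per group.

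Both reproduce with a two-sided test. A one-sided test would need 21 and 20.

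**Step 2: the smallest significant difference.** Standard error = 84.4 × √(2/25) = 23.9 min. An observed difference of 1.96 × 23.87 = 46.8 min is significant (48.0 min with the t distribution).

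**Step 3: false difference with no true effect.** Let T be true sleep, TIB time in bed and S scored sleep. Then S = sens × T + (1 − spec) × (TIB − T). With equal T in both arms, the false difference is (1 − spec) × (480 − TIB in A). The chance of significance in favour of B is Φ(false difference/23.87 − 1.96), which is 2.5% when there is no bias.

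| Group A time in bed | Extra in B | 20% scored as sleep | 40% | 60% |
|---|---|---|---|---|
| 420 min | 60 min | 12 min, 7% | 24 min, 17% | 36 min, 33% |
| 360 min | 120 min | 24 min, 17% | 48 min, 52% | 72 min, 85% |

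A noncentral t calculation gives slightly lower values: 31% rather than 33% at 36 min, and 84% rather than 85% at 72 min.

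**Step 4: what observed data could be explained away.** Solving the equation in Step 3 for T gives T = (S − (1 − spec) × TIB)/(sens + spec − 1). If sensitivity and specificity are the same in both arms, the corrected B–A difference is zero when 1 − spec = (difference in S)/(difference in TIB). With 120 min of extra time in bed, an observed 48 min vanishes at specificity 1 − 48/120 = 0.60, and 78 min at 1 − 78/120 = 0.35. With 60 min extra, 48 min vanishes only at 1 − 48/60 = 0.20, and no specificity explains 78 min. The by-arm time in bed therefore decides the question, and the plan does not report it.

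**The case against.** The case against has real force on size.

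- **No rates in the documents.** They give neither an actigraphy error rate nor a time in bed for Group A. Section III.a admits only people who report that they can spend 8 consecutive hours in bed, so Group A's habitual time may be near the upper end, where the bias is small.
- **All extra time as wake is extreme.** Section VII.d expects Group B participants to be awake for 24 hours or more after the first Intervention night shift. Much of their extra time in bed may well be sleep.
- **The laboratory result points the other way.** Section I.b reports higher sleep efficiency in the fixed 8-hour group. Under the model above, scored efficiency is (1 − spec) + (sens + spec − 1) × T/TIB, which falls when time in bed grows and sleep does not. The preliminary TST gap in Section VI.d is 403 − 221.4 = 181.6 min. Even if the ad lib group's time in bed were as short as its TST, a 60% share would explain at most 0.6 × (480 − 221.4) = 155 min.
- **The test is simplified.** The probabilities are for a two-sample comparison, not for the planned mixed model with repeated nights.
- **Time in bed is part of the intervention.** An imbalance in it is intended and is not itself a flaw.

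All of this stands as a limit on magnitude. It does not answer the gap. The laboratory recording method is not stated, laboratory results need not carry over to sleep at home, and the plan has no step that would show which situation the trial is in.

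A reader might infer three stronger things that the documents do not support. First, that sleep is measured by actigraphy alone: diaries are also kept, and it is only the calculation of TST and fragmentation that leaves them out. Second, that the artefact by itself would deliver Aim 1: that aim also requires fewer interruptions, and the direction for the fragmentation index is not established. Still wake could lower it and restless time in bed could raise it. Third, that TST will be inflated: the documents support only that it can be.

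**Conclusion.** The concern holds as a gap in the Aim 1 analysis of TST. The instruction that defines the intervention lengthens time in bed in B and C only, TST comes from a movement-based measure, and no planned analysis separates extra sleep from extra stillness. The possible bias favours the hypothesis for B–A and C–A and survives both randomisation and the baseline comparison.

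Its size cannot be fixed from the documents. Under the stated assumptions it runs from 12 min (about a 7% chance of a false result favouring B) to 72 min (about 85%), against 2.5% in that direction with no bias. The figures sit at the upper end because they treat all extra time in bed as wake. They do not show that a positive result would be false, and they are not the error rate of the planned mixed model. No claim is made for the fragmentation index.

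**What to change.** Amend the Aim 1 analysis text in Section VI.a–c:

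1. Derive time in bed for each main sleep episode from actigraphy together with the e-diary. Report time in bed, WASO (already a listed outcome) and sleep efficiency by arm beside TST.
2. Add a sensitivity analysis of the B–A difference in TST, using T = (S − (1 − spec) × TIB)/(sens + spec − 1) over a stated range of specificity. Report the specificity at which the difference disappears. If that value is plausible, qualify the conclusion that Group B slept longer.
3. Show e-diary TST as a descriptive cross-check only. It should not be a condition for the claim: it is unblinded self-report from participants who, under Section VIII.a, are paid $50 per day for keeping the assigned sleep episode.

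B versus C may be shown as supporting context, since both are assigned 8 hours in bed. It should be analysed as randomised, because the Aim 2b text reclassifies Group C participants who chose afternoon-evening sleep. It tests timing and cannot replace B versus A.

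The cost is a few extra tables, a specificity range that has to be assumed and justified, and possibly two or three diary items if sleep onset, wake time and time awake are not already collected.
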